### **Aim 1: I-HoME Protocol and Intervention Development**

**Synchronous Live Video – Patient Symptoms.** The patient symptom component of I-HoME will consist of weekly standardized assessment and management of signs/symptoms (e.g., pain, dyspnea, nausea, vomiting, agitation) experienced by the home hospice patient. In addition, visits on an as-needed basis (based on participant feedback and budget) can be requested by the patient, CG, and/or nurse interventionist, which may focus on a particular symptom or need. Development of the I-HoME protocol will focus on effectively evaluating and treating these symptoms along with other EoL symptoms through standardized assessments and management that incorporate education, non-pharmacologic and pharmacological therapies, and optimal use of hospice resources (e.g., respite, inpatient hospice care, etc.). A prototype intervention and manual of operations will be developed to incorporate existing best care practices and evidence-based research.

Doxy.me is a platform that will be used to conduct synchronous live video interactions between hospice nurses and patients/caregivers. Doxy.me is a secure and HIPAA compliant service. A business associate agreement will be obtained with Doxy.me prior to starting the study.

**Synchronous Live Video – CG Burden.** The CG component of I-HoME will focus on a weekly, standardized assessment and management of burden experienced by the CG. In addition, visits on an as-needed basis (based on participant feedback and budget) can be requested by the CG and/or nurse interventionist, which may address a particular type of burden. Development of the I-HoME protocol will focus on effectively evaluating CG burden and addressing it through education, skill building, coping strategy development, and optimal use of hospice resources (e.g., social work/spiritual care visit, respite, inpatient hospice care, etc.). A prototype intervention and manual of operations will be developed to incorporate existing best care practices and evidence-based research. Doxy.me is a platform that will be used to conduct synchronous live video interactions between hospice nurses and patients/caregivers. Doxy.me is a secure and HIPAA compliant service. A business associate agreement will be obtained with Doxy.me prior to starting the project/intervention.

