We will pilot patient participants (n=20) to answer a survey about their symptoms at baseline, 2 weeks, 4 weeks, and 6-weeks. The survey is the Edmonton Symptoms Assessment Scale (ESAS) which takes approximately 5 minutes to complete. We will also clarify to the patients that the ESAS data collected will not be shared with the clinical team and is for research purposes only. Enrollment of patients will help us understand the feasibility of interviewing hospice patients, and we will also analyze the differences in the ESAS scores from the dyad of caregiver and patient. Participants will be compensated a total of \$50 for their participation. The gift card will be mailed after they have given oral consent and completed the baseline survey questions over the phone. We are suggesting an alteration of written consent and the use of oral consent. The patients are in hospice care and will likely find in-person visits or other forms of written or electronic consents to be burdensome. Their participation involves no more than minimal risks to the subjects, and the oral consent

obtained over the phone will not adversely affect the rights and welfare of subjects. Whenever appropriate, subjects will be provided with additional pertinent information after participation.

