Hospice patients (n=20) will be referred by caregivers that are enrolled in the study. The study team will ask the caregiver if the patient would be open to participating. Patients with a hospice diagnosis of dementia will not be considered.

For the exit interviews, CGs must have completed at least one telehealth visit within the I-HoME randomized pilot study (Aim 3 intervention arm), be English speaking, and 18 years of age or older. Nurses must have had their patient's family CG receive at least one telehealth visit in Aim 3 intervention arm, be English speaking, and 18 years of age or older. Nurse practitioner interventionists must have delivered telehealth visits for the I-HoME study, must be English speaking, and 18 years of age and older.

**Aim 4:** Home hospice CGs (N=6) must be English speaking, 18 years of age or older, and not blind, and caring for a family member 18 years of age or older who is receiving home hospice care. Family CGs will also need to be providing caregiving (e.g., hands on care, care coordination) to the patient on a weekly basis. The target population for this study are CGs of terminally ill patients. While CGs don't need any prior experience in understanding the technology (televisits) being implemented, if the participant doesn't have the ability to use the technology after an initial session with one of the research team members, the CG will be excluded from the study. Participants recruited in Aim 4 will not be participants in Aim 1, 2, or 3 of the study.

**Procedures for recruiting study subjects.** Describe how potential study subjects will be approached. The protocol needs to include any telephone scripts or letters to be used for recruitment purposes, and incentives used to solicit participation.

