**Aim 3:** For the pilot RCT, I will be collaborating with VNS Health home hospice teams (each team consists of 5-7 nurses). These two teams will be randomized to receive the intervention (I-HoME) or standard care at the nursing level. Since this is a pilot study and the primary aim is to assess for intervention feasibility, we acknowledge that we will not be able to control for certain differences. We will work with VNS Health hospice leadership to select hospice teams that serve similar patient populations. In both hospice teams, family CGs will be screened for study eligibility within 7 days of their home hospice admission through chart review. Screening will be conducted regularly by the research team. Prior to reaching out to potential participants, the

research team will contact the nurse caring for the patient and CG to confirm that it would be appropriate to contact the CG for the study. Weill Cornell and VNS Health are co-engaging one or more research staff through a subaward – they will be hired by VNS Health and performing the initial screening/recruitment. VNS Health staff will contact subjects by phone to inquire about their interest in participating (see telephone script C and D). If there is interest expressed by the CG over the phone, a research team member will reach out to conduct an in-home visit to describe the study and obtain written informed consent.

No external investigators (unless they are a VNSNY employee or VNSNY volunteer/intern) will be given names or contact information until subject approval is obtained through a VNSNY provider.

Hospice patients (n=20) will be referred by caregivers that are enrolled in the study. The study team will ask the caregiver (after they have been consented) if the patient would be open to participating in the study to provide ratings on their symptoms. Patients with a hospice diagnosis of dementia not be considered for the study. Eligible patients will be contacted by phone by a research team member.

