There is a minimal risk of subject distress during the administration of surveys (see Appendix B) to patients and CGs during the pilot phase in Aims 2 and 3. As a result, I will have safeguards in place to address subject's distress. All study subjects will be free to refuse to answer any questions or to discontinue study participation at any time. In all cases where there might be concerns for suicidality, referrals to a hotline and mental health services will be provided. In addition, the PHQ-9 will be administered to the subject. If subjects do not answer "not at all" to question 9 in the PHQ-9 survey, the research team member will remain with the participant and call to a trained professional to speak with the participant to create a safety plan which may include a call to 911 if warranted.

For studies that require a DSMB, a **DSMB plan** should be provided in the protocol which should include: number of members, meetings (how often), data that will be reviewed during the meetings and plan regarding dissemination of summary reports (i.e. meeting minutes) to the IRB.

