#### Safety Alerts

- Severe medical problem of caregiver
- Patient and/or caregiver abuse
- Patient and/or caregiver threatens to harm him or herself or others

A summary of all serious adverse events and safety alerts (i.e., those that are anticipated and related to the study) will be reported to the NIA Program Officer and Safety Officer quarterly, unless otherwise requested by a Safety Officer.

When serious adverse events occur that are unanticipated (i.e., events that are not listed above) and are related to the study (i.e., there is a reasonable possibility that the incident, experience, or outcome may have been caused by the procedures involved in the research), they will be reported to the NIA Program Officer within 48 hours of the study's knowledge. Unanticipated problems involving risks to study participants or others will also be reported to NIA within 48 hours. Unanticipated problems are defined as any incident, experience, or outcome that is unexpected given the research procedures that are described in the protocol-related documents; related or possibly related to participation in the research; or suggest that the research places participants at a greater risk of harm than was previously known or recognized.

[name], the PI, will be responsible for ensuring participants' safety on a daily basis. He will also evaluate the progress of the study, review procedures for maintaining the confidentiality of data, the quality of data collection, management, and analyses.

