### A.2 Frequency of Data and Safety Monitoring

When an alert or adverse event is identified by a member of the research team, the event must be reported to [name] within 24 hours and recorded on the Alert/Adverse Event Form in the study's REDCap database. [name] will report any adverse events related to the study to the Weill Cornell Medicine IRB and the VNSNY IRB, according to IRB policy. When serious adverse events occur that are unanticipated (i.e., not listed in the Data and Safety Monitoring Plan) and that are related to the study, they will be reported to the NIA Program Officer within 48 hours of the study's knowledge of the serious adverse event.

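### Aim 3 patients are told their ESAS answers will not reach the clinical team, with no stated exception, and the protocol text gives no route to the hospice team for a severe physical symptom

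*Combined protocol and SAP*

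**What the plan says.** The Aim 3 section on adding patient participants plans ESAS surveys of 20 home hospice patients at four times. It says patients will be told that "the ESAS data collected will not be shared with the clinical team and is for research purposes only". The same paragraph gives no threshold, exception or option for the patient to agree to sharing. On recruitment, the Aim 3 text under sample selection states: "Hospice patients (n=20) will be referred by caregivers that are enrolled in the study". The Aim 3 text under recruitment procedures adds: "Eligible patients will be contacted by phone by a research team member". Patients with a hospice diagnosis of dementia are not considered.

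Safety handling is described in two other places. The statement of risks and benefits says: "In all cases where there might be concerns for suicidality, referrals to a hotline and mental health services will be provided". It adds a live response tied to item 9 of the PHQ-9. Section A.1 of the Data and Safety Monitoring Plan lists the events that trigger a formal response. Its one medical alert is "Severe medical problem of caregiver"; patients appear only under abuse and threats of harm. On reporting, A.1 says: "A summary of all serious adverse events and safety alerts (i.e., those that are anticipated and related to the study) will be reported", with the NIA Program Officer and Safety Officer as recipients. Section A.2 begins: "When an alert or adverse event is identified by a member of the research team, the event must be reported to" and then names a person, evidently the PI, with a 24-hour limit and a database form. The IRBs and NIA follow.

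**The concern.** The ESAS asks dying patients how bad their symptoms are, so a severe answer is foreseeable. A research team member who hears or receives one has, on the page, a stated rule against passing the data to the clinical team and no instruction pointing the other way. A patient may tell only the researcher about a symptom that could be treated the same day.

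The gap matters most in the control arm. Intervention families also have "weekly standardized assessment and management of signs/symptoms" through the study's video visits, plus as-needed visits as funding allows. Control families do not have those study visits.

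The no-sharing sentence has a proper use: it warns patients that the survey is not a channel for reporting symptoms. What the protocol text lacks is the other half of that message, which is to call the hospice.

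**Working it through.** The plan gives no figure on this point to reproduce. The check has three parts.

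**1. Is there a route to the hospice team?** Each safeguard in the protocol text, with its trigger and recipient:

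- Patient add-on, Aim 3: no trigger for a severe score. A general line about giving subjects pertinent information after participation is not an escalation step.
- Statement of risks and benefits: subjects may refuse questions or stop. The active steps are for suicidality and PHQ-9 item 9.
- A.1, serious adverse events: all four listed events concern the caregiver.
- A.1, safety alerts: the medical alert concerns the caregiver. Abuse and threats of harm can concern the patient.
- A.1 and A.2, recipients: PI, two IRBs, NIA Program Officer and Safety Officer. The hospice nurse or team is not named.
- Aim 1, patient symptoms: extra visits can be requested by the patient, caregiver or interventionist. They belong to I-HoME and are not triggered by an ESAS answer.

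No item sends a patient's severe physical symptom to the hospice team.

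**2. How many surveys are involved?** Inputs: 20 patients and 4 assessments, from the patient add-on. Maximum: 20 × 4 = 80.

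Deaths lower this. The power paragraph uses mortality of 35% at four weeks and 62% at eight weeks. With a constant hazard within each interval (assumption):

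- S(2) = 0.65^0.5 = 0.806
- S(4) = 0.650
- S(6) = (0.65 × 0.38)^0.5 = 0.497
- Surveys per patient = 1 + 0.806 + 0.650 + 0.497 = 2.953
- All patients: 20 × 2.953 ≈ 59

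This assumes that general hospice mortality applies to patients able to be interviewed and that every survivor answers. The unit is surveys, not calls. Phone is explicit only for the patients' baseline survey. The Aim 3 measurement paragraph describes phone administration by a research assistant, but the Aim 3 introduction and the risk statement also allow electronic follow-up. Neither 80 nor 59 measures harm.

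**3. What could a handoff do to the arm comparison?** Caregiver-reported patient symptoms are an Aim 3 efficacy outcome. If k control patients are handed off and each improves by g SD, the control mean shifts by (k/50) × g. The plan gives neither k nor g. With g = 0.5 (assumption):

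- k = 10 (20 patients split evenly, assumption): (10/50) × 0.5 = 0.10 SD
- k = 20 (all patients in the control arm): (20/50) × 0.5 = 0.20 SD

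The plan's detectable effects run from d = 0.57 to d = 0.8. The shift scales with g, so these figures illustrate the size and do not bound it.

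**The case against.** The strongest reply is that the absence cannot be proved. The paragraph summarises what patients will be told; it is not the script. The consent text, telephone scripts and Appendix B were not available. Section C.6 leaves the procedures for identifying and reporting events to the safety monitor's first meeting. A reminder to call the hospice may already be in place, and it would not contradict the no-sharing sentence. That stands. It does not rescue a handoff step, which would conflict with an unqualified promise not to share.

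Second, other text narrows the gap. A.1 defines adverse events broadly enough that a severe symptom found at a follow-up assessment could be reported to the PI within 24 hours, and it makes the PI responsible for participants' safety each day. The research team already contacts the patient's own nurse before recruitment. Caregivers in both arms report patient symptoms weekly. Patients able to answer a survey can often call the hospice themselves. All of this lowers the risk, but none of it tells the person administering the survey what to do.

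Third, a notice that severe scores may be passed on could change what patients report, which bears on the planned patient–caregiver ESAS comparison. This is a real cost of the fix.

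A reader might infer that staff would ignore a patient in distress, or that control patients are left without symptom care. The documents do not support either. The sentence withholds research data and does not forbid advising the patient, and the control arm receives home hospice services as usual.

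**Conclusion.** The point holds as a stated rule that needs an exception. Followed as written, the no-sharing sentence stops a severe ESAS report from reaching the hospice team, and no other part of the protocol text overrides it.

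The risk is limited, for three reasons: usual hospice care continues in both arms, every ESAS patient comes through an enrolled caregiver, and hospice diagnoses of dementia are excluded. Exposure is at most 80 surveys, or about 59 under the plan's mortality and the assumptions above. The number of severe symptoms told only to the researcher cannot be estimated from the documents, so no claim of patients harmed is warranted. Nor can it be said that no reminder or procedure exists anywhere in the trial's materials.

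This is a cheap improvement to patient safety, held with medium confidence because the scripts and consent text were not available.

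**What to change.** 1. Amend the sentence in the patient add-on to say, in substance: answers are not shared routinely; if you report a severe symptom we will, with your agreement, tell your hospice nurse the same day. The hospice clinical lead sets the threshold. If the patient declines, the answer is not passed on. The existing responses to suicidality, abuse and threats of harm stay as they are.
2. End every ESAS survey, by phone or online and in both arms, with a reminder to call the hospice about any symptom that needs attention.
3. Log handoffs by arm, apart from the quarterly safety-alert summary, because severe symptoms are expected in hospice.

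The cost is one amendment, one closing line in the script or form, and a short log; the contact with the patient's nurse already exists. There are two downsides. Handoffs could slightly dilute the arm contrast in up to 20 of the 100 dyads, which the log makes visible. Patients may also report severe scores differently once told of the handoff, which should be noted when the patient–caregiver ESAS comparison is interpreted.

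The Aim 4 rationale refers to data already collected, so the ESAS surveys may be over. If they are, confirm instead how severe reports were handled.

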### **Addition of exit interviews for Aim 3**

We will ask caregivers who participated in the Aim 3 randomized pilot study, nurses of these caregivers' care recipients, and the nurse practitioner interventionists who conducted the telehealth visits to complete a recorded phone interview asking about their experiences with the I-HoME program. The interview will take approximately 30-45 minutes for the caregivers, 10-15 minutes for the nurses, and 30 minutes for the interventionists. The interviews will be transcribed and anonymized to destroy any identifying information upon transcription. The questions asked are listed in Interview – Aim 3 documents below. The in-depth qualitative interviews will help us understand the feasibility and acceptability of the I-HoME intervention and ways to modify the intervention to make it more helpful for caregivers. Participants will be compensated \$50 for their participation. The gift card will be mailed after they have given oral consent and completed the phone interview. The oral consent obtained over the phone will be less burdensome than other forms of written or electronic consents. The participation involves no more than minimal risks to the subjects, and the oral consent obtained over the phone will not adversely affect the rights and welfare of subjects.

### **Aim 4: Modified I-HoME single armed pilot study**

The aim of the single-armed pilot study will be to examine the feasibility of providing I-HoME over the course of 3-weeks. This would include 2 tele-visits per week for up to 3 weeks instead of Aim's 3 weekly televisit over the course of 6 weeks. Our rationale for pilot testing this is to address the attrition concerns encountered in the existing data collected. While we found administering the tele-visits feasible, we also noticed that many caregivers didn't complete the six-week intervention (this was mainly because their loved one passed away earlier, so they didn't get the full benefit of the 6 visits). In Aim 4, we will pilot test a 3-week program, delivering 6 televisits, and examine its feasibility.

**Intervention.** A nurse practitioner interventionist will deliver the I-HoME intervention through a televisit twice a week for up to 3 weeks. The study team will conduct a phone call with the CG at the start of the study to obtain verbal consent and train the CG on accessing the televisit platform. Participants will also be mailed a user guide and have access to technical assistance if software concerns arise or if an adverse event occurs. Software by Doxy.me will be used to conduct HIPAA compliant synchronous video visits. Phone visits will be conducted if video visits are unable to be done due to hardware or software issues.

**Measurements.** All participants will be assessed on the measures listed in Table 3. Baseline CG demographic data will be collected during after consent and an exit interview will be conducted by phone when the participant completes the study. Participants will be compensated \$50 for the initial survey, and \$50 for the exit interview.

Table 3. Study measures for Aim 4

Caregiver
Age
Gender
Race/ethnicity
Religion
Education
Relationship to patient
Hours providing care to patient
Number of CGs caring for the patient
Occupation
Income

**Sample selection/ Data sources.** Describe characteristics of the subject population, such as their anticipated number, age, sex, ethnic background, and state of health. Identify criteria for inclusion or exclusion. If excluding certain racial or ethnic groups, please explain rationale and how exclusion may limit generalizability of findings. Explain the rationale for use of special classes of vulnerable subjects, such as pregnant women, children, mentally impaired, especially those whose ability to give voluntary informed consent may be in question. If vulnerable populations are to be used, investigators must deal thoroughly with the potential risk. If you need access to HIPAA-defined protected health information (*PHI-see attached list*) in order to screen for potential participation, for secondary data analysis or for other purposes and you do not plan to get authorization for access to this data from each individual you must request a *waiver of authorization* (see instructions below).

**Aim 1:** Home hospice providers (N=10) and family CGs (N=10) must be English speaking, 18 years of age or older, not blind, and either providing or receiving home hospice care. Home hospice patients (N=10) must be English speaking, 65 years of age or older, not blind, and enrolled in home hospice care. Patients with a terminal diagnosis of dementia or patients who have cognitive impairment and unable to sign a written/electronic informed consent will be excluded. A member of the research team will conduct this evaluation of the prototype at the patient's and/or CG's residence or through video conference. For home hospice provider participants, the user centered design visit will be conducted at VNSNY headquarters or through videoconference. All participants will be required to sign a written informed consent/electronic consent.

Each participant will be trained on the use of the prototype I-HoME care intervention. Specifically, participants will be asked about content, usability, feasibility/implementation concerns, anticipated challenges/benefits, and design features (**Appendix A**) after being shown the prototype. The aim of this process is to discover issues that users may have with the intervention. Information gathered as part of this process will be used to refine the intervention, which will include a manual of operations and educational videos before pilot testing begins. Study participation is expected to last 1-2 hours and subjects will be compensated with a gift card for their time.

Recruitment of subjects for this Aim is detailed further in this protocol. Participants recruited in Aim 1 will not be able to participate in Aim 2 or 3 of the study.

**Aim 2:** Home hospice CGs (N=10) must be English speaking, 18 years of age or older, not blind, and caring for a family member 65 years of age or older who is receiving home hospice care. Family CGs will also need to be providing 10 hours of hands on caregiving to the patient. The target population for this study are CGs of terminally ill patients. While CGs don't need any prior experience on how to use a tablet or understand the technology being implemented, if the participant doesn't have the ability to use the technology after an initial session with one of the research team members, the CG will be excluded from the study.

Recruitment of subjects for this Aim is detailed further in this protocol. Participants recruited in Aim 2 will not be able to participate in Aim 3 of the study.

**Aim 3:** Home hospice CGs (N=100) must be English speaking, 18 years of age or older, not blind, and caring for a family member 50 years of age or older who is receiving home hospice care. Family CGs will also need to be providing caregiving (e.g., hands on care, care coordination) to the patient on a weekly basis. The target population for this study are CGs of terminally ill patients. While CGs don't need any prior experience on how to use a tablet or understand the technology being implemented, if the participant doesn't have the ability to use the technology after an initial session with one of the research team members, the CG will be excluded from the study.

Recruitment of subjects for this Aim is detailed further in this protocol. Participants recruited in Aim 3 will not be participants in Aim 1 or 2 of the study.

Hospice patients (n=20) will be referred by caregivers that are enrolled in the study. The study team will ask the caregiver if the patient would be open to participating. Patients with a hospice diagnosis of dementia will not be considered.

For the exit interviews, CGs must have completed at least one telehealth visit within the I-HoME randomized pilot study (Aim 3 intervention arm), be English speaking, and 18 years of age or older. Nurses must have had their patient's family CG receive at least one telehealth visit in Aim 3 intervention arm, be English speaking, and 18 years of age or older. Nurse practitioner interventionists must have delivered telehealth visits for the I-HoME study, must be English speaking, and 18 years of age and older.

**Aim 4:** Home hospice CGs (N=6) must be English speaking, 18 years of age or older, and not blind, and caring for a family member 18 years of age or older who is receiving home hospice care. Family CGs will also need to be providing caregiving (e.g., hands on care, care coordination) to the patient on a weekly basis. The target population for this study are CGs of terminally ill patients. While CGs don't need any prior experience in understanding the technology (televisits) being implemented, if the participant doesn't have the ability to use the technology after an initial session with one of the research team members, the CG will be excluded from the study. Participants recruited in Aim 4 will not be participants in Aim 1, 2, or 3 of the study.

**Procedures for recruiting study subjects.** Describe how potential study subjects will be approached. The protocol needs to include any telephone scripts or letters to be used for recruitment purposes, and incentives used to solicit participation.

**Aim 1:** VNS home hospice providers will be recruited via email provided by VNSNY hospice collaborators (see email recruitment template). Hospice providers who respond to the email with interest in participating will be scheduled for an in-person meeting at VNSNY headquarters or via video conference (e.g., Zoom – HIPAA compliant, Doxy.me) to describe the study and obtain written/electronic informed consent. Electronic informed consent will be obtained through Doxy.me or DocuSign which are both HIPAA compliant and have electronic signature capabilities) Interviews will either be done individually or in focus groups. Signed electronic consents will be stored on a secure Weill Cornell server. Zoom and Doxy.me provides a secure HIPAA compliant platform to conduct synchronous video meetings.

One hospice team will work with a VNSNY-supervised research assistant (RA) and the PI to identify potential patient/CG participants that meet criteria (based on inclusion/exclusion criteria) for Aim 1. Weill Cornell and VNSNY are co-engaging one or more RAs – they will be hired by Weill Cornell but will also be brought on as an intern or volunteer at VNSNY. The RA(s) will go through VNSNY orientation processes and HIPAA training. In their VNSNY site role, the RA or the PI will contact subjects to briefly describe the project by phone (see telephone script A) or via video conference (e.g., Zoom, Doxy.me). The PI's role in recruiting patients and caregivers will happen after a VNSNY staff person or the RA co-hire receives permission from the patient to release their name and contact information for the study. Patient and CGs interested in participating will be scheduled for an in-home visit or via video conference (e.g., Zoom, Doxy.me) to describe the study and obtain written/electronic informed consent. Electronic informed consent will be obtained through Doxy.me or DocuSign which are both HIPAA compliant and have electronic signature capabilities. The RA or PI will transmit participant data to Weill Cornell through the VNSNY approved secure web portal.

No external investigators (unless they are a VNSNY employee or VNSNY volunteer/intern) will be given names or contact information until subject approval is obtained through a VNSNY provider.

**Aim 2:** For the single armed pilot phase, I will be collaborating with home hospice teams (each team consists of 5-7 nurses taking care of patients in a certain region of NYC). Family CGs will be screened for study eligibility within 7 days of their home hospice admission through chart review. Screening will be conducted regularly by the research team. Prior to reaching out to potential participants, the research team will contact the nurse caring for the patient and CG to confirm that it would be appropriate to contact the CG for the study. Weill Cornell and VNS Health are co-engaging one or more research staff through a subaward – they will be hired by VNS Health and performing the initial screening/recruitment. VNS Health staff will contact subjects by phone to inquire about their interest in participating (see telephone script B). The RA will be educated about the I-HoME intervention and answer questions that subjects may have during the phone call. If there is interest expressed by a CG over the phone, a research team member will reach out to conduct an in-home visit or phone call to describe the study and obtain written or oral informed consent (based on CG preference). Participants will be provided a copy of the informed consent after consent is obtained (in-person or it will be mailed to them).

We will also be implementing a flyer to help recruit participants for the study. The flyer will be provided to hospice nurses to distribute to CGs they feel would be appropriate for the study. The flyer will provide a number for CGs to call if they are interested in participating. CGs that meet the inclusion and exclusion criteria will be consented to participate in the study by the research team.

No external investigators (unless they are a VNS Health employee or VNS Health volunteer/intern) will be given names or contact information until subject approval is obtained through a VNS Health provider.

**Aim 3:** For the pilot RCT, I will be collaborating with VNS Health home hospice teams (each team consists of 5-7 nurses). These two teams will be randomized to receive the intervention (I-HoME) or standard care at the nursing level. Since this is a pilot study and the primary aim is to assess for intervention feasibility, we acknowledge that we will not be able to control for certain differences. We will work with VNS Health hospice leadership to select hospice teams that serve similar patient populations. In both hospice teams, family CGs will be screened for study eligibility within 7 days of their home hospice admission through chart review. Screening will be conducted regularly by the research team. Prior to reaching out to potential participants, the

research team will contact the nurse caring for the patient and CG to confirm that it would be appropriate to contact the CG for the study. Weill Cornell and VNS Health are co-engaging one or more research staff through a subaward – they will be hired by VNS Health and performing the initial screening/recruitment. VNS Health staff will contact subjects by phone to inquire about their interest in participating (see telephone script C and D). If there is interest expressed by the CG over the phone, a research team member will reach out to conduct an in-home visit to describe the study and obtain written informed consent.

No external investigators (unless they are a VNSNY employee or VNSNY volunteer/intern) will be given names or contact information until subject approval is obtained through a VNSNY provider.

Hospice patients (n=20) will be referred by caregivers that are enrolled in the study. The study team will ask the caregiver (after they have been consented) if the patient would be open to participating in the study to provide ratings on their symptoms. Patients with a hospice diagnosis of dementia not be considered for the study. Eligible patients will be contacted by phone by a research team member.

For the exit interviews, family CGs who participated in the pilot RCT (Aim 3) will be screened for study eligibility. VNS Health staff will contact eligible CGs by phone to inquire about their interest in participating (see telephone script E). If there is interest expressed by the CG over the phone, a research team member will reach out to complete the verbal consent and recorded phone interview. Nurses and nurse practitioner interventionists will be contacted via email to inquire about their interest in participating (see email template F and G). If there is interest expressed, a research team member will reach out to complete the verbal consent and recorded phone interview.

**Aim 4:** This study will involve collaboration with VNS Health home hospice teams. Family CGs will be screened for study eligibility within 7 days of their home hospice admission through chart review. Screening will be conducted regularly by the research team. Prior to reaching out to potential participants, the research team will contact the nurse caring for the patient and CG to confirm that it would be appropriate to contact the CG for the study. VNS Health staff will contact subjects by phone to inquire about their interest in participating (see telephone script H). The RA will be educated about the I-HoME intervention and answer questions that subjects may have during the phone call. If there is interest expressed by a CG over the phone, a research team member will describe the study, obtain verbal informed consent, administer demographic questions, and train CGs how to access the telehealth platform. Participants will be mailed a copy of the informed consent after consent is obtained. No external investigators (unless they are a VNSNY employee or VNSNY volunteer/intern) will be given names or contact information until subject approval is obtained through a VNS Health provider.

**Consent forms and additional PHI authorizations.** A person *consents to participate in research* and *authorizes use and disclosure of protected health information*. Consent forms should be clear, easy to understand, and written at a recommended fifth grade reading level. If children under 18 years of age will be included in the study, then parental consent may also be required. If consent forms are not deemed necessary, the rationale for this should be included in the statement of protection of human subjects in the proposal body. The investigator is responsible for retaining signed consents in the research files. Because a consent form documents an agreement between two parties, the subject should be given a copy to keep as well. *A list of elements required in an informed consent form is attached along with a prototype consent form.* If protected health information (PHI) will be recorded for patients consenting to research then additional elements need to be included in the consent or a separate authorization is required. Minimal requirements for an authorization form are on page 6 of this application packet.

**Data to be employed**, data collection procedures, data collection instruments, if applicable (okay to submit instruments in draft form).

Please see Table 2, Appendix A and Appendix B for data collection instruments at the end of the document. Data collection procedures will be conducted by trained research staff and done in-home, at VNSNY headquarters, by phone, by videoconference or online surveys as outlined in the protocol above.

